## PROJECT SUMMARY

Malaria poses a serious burden in sub-Saharan Africa. Efforts are ongoing to scale up interventions that work. These include the use of Long Lasting Insecticidal Nets (LLIN), Intermittent Preventive Treatment in children (IPTc), and test, treat and track (TTT). There is the need, however, for mass testing, treatment and tracking (MTTT) of the whole population to reduce the parasite load before implementing the aforementioned interventions. Though, Seasonal Malaria Chemoprophylaxis (SMC) is adopted for selected localities in Ghana, the impact of such interventions could be enhanced, if associated with MTTT in order to reduce the parasite load at baseline. MTTT of children in Ghana has demonstrated a parasite load reduction from 25% to 1%. However, unanswered questions include - could this be scaled up? What proportion of the community could be covered over a given time? What do the investigators need to accomplish large scale MTTT? In designing interventions that aim at reducing the burden of malaria in children under five, for example, MTTT has largely been left out. Adults who are not often targeted by such interventions remain reservoirs that fuel transmission. This study explores the scale-up of interventions that work using existing community volunteer teams to lower cost. These volunteers will play a surveillance role by conducting home-based management of malaria. To avoid challenges posed by stockouts, short message service (SMS) will be used to monitor the level of stocks for malaria medicine and Rapid Diagnostic Tests (RDTs). It is hypothesized that there are more asymptomatic malaria cases (those who carry the parasite but are not ill) than symptomatic cases reported by hospital records in the Pakro sub district and that, carrying out MTTT in combination with home-based management of malaria in specific communities could greatly reduce the burden. Through this study, the bottlenecks that hinder scaling-up of MTTT will be documented in order to facilitate the process.

## **Stakeholders**

Ghana Health Service, Noguchi Memorial Institute for Medical Research (NMIMR), the local communities and WHO.

## **Introduction/Rationale**

The World Health Organization (WHO) in 2010 reported that malaria was endemic in 96 countries reflecting an improvement of the situation of 2005 where it was endemic in 106 countries (WHO, 2010). Malaria morbidity and mortality remain a serious problem in sub Saharan Africa especially in areas with holo-endemic transmission (Appawu, Baffoe-Wilmot et al. 1994). Over the last decade, the number of recorded malaria cases has steadily dropped from 247 million cases with 881,000 deaths reported in 2006 to 198 million with 584,000 deaths in 2013 (WHO, 2009, 2010, 2013). This has largely been due to the introduction of ACTs following the resistance witnessed against chloroquine as well as an increase in the number of control measures such as the use of insecticide treated nets, long lasting insecticidal nets (LLIN), vectors surveillance and intermittent preventive treatment in pregnancy (IPTp) and implementation of the WHO policy on test, treat and track (WHO, 2012). Despite the reported decrease, most of the endemic countries across sub Saharan Africa still bear the greatest burden of the disease where 90% of the deaths are reported with more than 75% of the mortalities in children under five (WHO, 2014).

Ghana National Malaria Control Programme (GNMCP) reports reveal that in 2006 malaria accounted for 37.5% of all out patient consultations, 36.0% of all hospital admissions, and about 33.4% of all mortality in children under age five years. Following the recommendation of the WHO, Ghana changed its malaria treatment guidelines adopting artesunate and amodiaquine as first line for the treatment of uncomplicated malaria to replace chloroquine (GNMCP, 2006). By 2012, hospital statistics across the country revealed that malaria was responsible for 38.93% of the

outpatient consultations and 38.80% of admissions. Of those admitted for malaria, 63% were children under 5 years of age while pregnant women constituted 16.8%. Furthermore, According to the Ghana Health Service (GHS) report of 2012, malaria accounted for 22.4% deaths in children less than five years of age and 3.4% deaths among pregnant women (GHS, 2012). Over the last decade, studies in Ghana have demonstrated that artesunate and amodiaquine combinations are not only efficacious in clearing the malaria parasites from patients (Koram et al. 2008) but if used for intermittent preventive treatment programmes for children under five could effectively clear more than 90% of the parasite in this age group (Ahorlu et al. 2009).

Different studies have demonstrated very high level of asymptomatic malaria parasitaemia in both less than 5 years old and school age children. In 2009, Ahorlu et al, reported a parasite prevalence of 25% in less than five year old children in the Shime sub district in the coast of Ghana. In the same light, (Otupiri et al. 2012) reported a malaria parasitaemia prevalence of 58.6% among school children in the Ejusu Juaben District, while (Sarpong et al. 2015) reported a 41.5% prevalence of malaria parasitaemia in Ghanaian school children in the Ashanti and Upper West regions of the country. A related study in the Dodowa area demonstrated that children with high levels of asymptomatic parasitaemia have a higher risk of coming down with clinical malaria (Ofosu-Okyere et al. 2001).

The link between one parasite carrier or infected individual and the next relies on the mosquito picking up the parasite during a blood meal. This means that even if all patients with malaria are treated of the disease, those individuals who carry the parasite and are not ill could redistribute it to the healthy population with the help of the mosquito and therefore, the cycle simply continues. The high incidence of asymptomatic parasitaemia serves as a reservoir that fuels the malaria transmission cycle (Bousema et al. 2014 et al. 2016). If the parasite is cleared from the blood of asymptomatic individuals as well as the sick patients with the very efficacious Artemisinin-based Combination Therapy (ACT), then, even the most effective mosquito vector would have nothing to transmit following a blood meal (Ahorlu et al. 2011).

Continuous exposure to the malaria parasite has led to the development of immunity, especially in adults in endemic areas. This is often a slow process as it depends on repeated exposure to the parasites (Greenwood, 1987, Njama-meya et al., 2004).

This explains why children carry the greatest burden of the disease. As they grow beyond age 5 years, the prevalence of malaria or parasitaemia in this group begins to decrease following the development of immunity to the parasite (Bull et al. 1998). Age, therefore, has a great role to play when looking at the dynamics of the malaria burden. A study of trends in malaria admission in a Health Centre in Cameroon has demonstrated that the variation in the prevalence of malaria effectively reflected a variation in the prevalence in children age one to less than 15 years (Ndong et al. 2014). In endemic areas, children have been reported to harbour relatively high levels of the parasite without coming down with the disease (Snounou et al. 1997), and the population is continuously exposed to the infected mosquitoes. That is, the already parasitised individuals can be re-infected either with the same parasite, thus, increasing the parasite load or other parasite species leading to a co-infection in areas with more than one species of *Plasmodium*. On the other hand, the uninfected mosquito is initially harmless even if it bites. However, it becomes infective when infected by a parasitised individual who could either be febrile or asymptomatic. Therefore, while enormous effort is being made to prevent man-vector contact through the use of treated nets, the benefits from using these nets could be amplified if such programmes integrate mass parasite clearance as part of their agenda. That is mass testing, treatment and tracking should precede the mass distribution of LLIN in a given area or intermittent preventive treatment in children.

There has been concerted effort in the past decade to evaluate the possible effects of massive parasite clearance using intermittent preventive treatment in less than five year old children in different part of Africa with interesting results. Most studies however, focused on the clinical incidence of the disease as outcome measure which has been observed to reduce with a range of between 20-80% depending on a number of factors (Dicko et al. 2008, Kweku et al. 2009). In a longitudinal study in a Coastal village in Ghana, Ahorlu et al, demonstrated that associating IPTc with home based management of malaria by community workers could clear more than 90% of the parasite pool in the community. This intervention reduced malaria parasitaemia prevalence from 25% at baseline to 1% at evaluation using artesunate and amodiaquine. This low level of parasitaemia in the study population was found to persisted over a period of two years (Ahorlu et al. 2011). Though, this intervention had targeted only under 5 years children, it revealed the potential role intermittent preventive treatment of the population could play in reducing malaria prevalence and

consequently paving the way for malaria elimination. Given that old members of the household are likely to have some immunity to the malaria parasite, they however, represent the reservoir that refuels the parasite pool whenever it is reduced by IPTc. Therefore, for sustainability of such implementation intervention, intermittent preventive treatment would be of greater benefit if all the members of each given household are targeted for mass testing, treatment and tracking at baseline and consequent prompt home-based treatment for suspected cases. Bearing in mind that huge resources are required for IPT of whole communities, it has been suggested that mass screening of whole communities be carried out once a year while IPTc be conducted regularly in combination with the home based management (Ahorlu et al. 2011). This could further enhance the efforts.

Implementation of rapid scale-up preventive interventions in the past decade has led to a reasonable decrease in the burden of the malaria (WHO 2011) especially given the introduction of the WHO policy of test, treat and track (T3) (WHO 2012). The challenges involved with translating research scenarios into implementation are enormous. It is important to understand the bottlenecks that hinder this process in order to undertake mass testing, treatment and tracking in a large scale using existing health systems, especially in an era when global funding for health services is slowing down (Rao et al. 2013).

Any effective control strategy that interrupts the link between man, the parasite and the vector could seriously reduce the transmission of malaria. In this light, interventions focused on clearing of the parasites in asymptomatic individuals in combination with intensive use of other control measures could pave the way for pre-elimination of the parasite in endemic communities (Bousema et al. 2014). This study aims at reducing the asymptomatic parasitaemia in the Pakro sub district of the Eastern Region of Ghana by conducting MTTT for malaria parasitaemia among household members of age 6 months and older and carrying out targeted treatment of all cases with confirmed asymptomatic parasitaemia or clinical malaria. These interventions intend to follow up enrolled participants over a period of two years. Hospital records will also be studied to document trends in malaria admissions and occurrence of other diseases in the area before and after the interventions.

## **Rationale**

Malaria continues to pose a serious burden to the local populations in sub-Saharan Africa. Several efforts have been made to scale up interventions that work such as preventing man-vector contact, intermittent preventive therapy, seasonal malaria chemoprophylaxis as well as TTT for febrile patients (WHO, 2012). However, much still has to be done to target the mass testing, treatment and tracking of whole populations in order to reduce the parasite load before implementing the above mentioned interventions. Though SMC is adopted for selected localities in Ghana, MTTT could be used to drastically bring down the parasite load in a given population before the implementation of interventions such as SMC. Elsewhere, it has been demonstrated that incorporating the antimalarials in vaccination programmes could delay the first malaria episode in children under five ([Dicko et al., 2008](#)).

Furthermore, MTTT of children in a community in Ghana has been reported to reduce the parasite load in a given community from 25% to 1% (Ahorlu et al., 2011). The questions that remain are - could this be scaled up? What proportion of the community could be covered over a given time? What will it take to accomplish MTTT in large scale? In designing interventions that aim at reducing the burden of malaria in children under five, for example, MTTT could be used to clear parasites from the general population before the interventions are implemented. This is because the adults who are not often included in the interventions that target children under 5 years old tend to act as reservoirs that fuel the transmission. To solve the problem of personnel who are limited at the level of the health service and coverage, this study will be making use of the existing network of community nurses/volunteer teams that are used during vaccination programmes. These volunteers, who reside in the communities, will carry out the interventions in the given communities and conduct the home-based management of malaria between interventions thereby increasing surveillance and reducing cost. Furthermore, to solve the problem of stock-outs and quality of the RDTs and antimalarials, the investigators will make use of SMS through mobile phones and a team will conduct monthly monitoring and evaluation of the field activities of the volunteers as well as refill the medicine and RDTs. The volunteers will be trained based on the 2014 guidelines for managing uncomplicated malaria.

The investigators hypothesize that in the Pakro sub district, there are more asymptomatic malaria cases than the symptomatic cases reported by hospital records and that if the investigators carry out MTTT in combination with home-based

management of malaria in specific communities over two years, a large proportion of the parasite reservoir will be cleared and consequently open up possibilities for pre-elimination of malaria in the area. It is also intended that the bottlenecks involved in scaling up mass testing, treatment and tracking will be documented in order to facilitate the process.

### **Main objective**

The main objective of this study is to explore the impact of scaling up mass testing, treatment and tracking on malaria prevalence among children under fifteen years of age in the Pakro sub district of Ghana.

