### **Study Design:**

This is an Implementation Research (IR) with a longitudinal cohort design to be undertaken within a two year frame work. The interventions are designed to compare the baseline to evaluation findings following the modified protocol of (Ahorlu et al., 2011). **There are two components to this implementation study a). The longitudinal (cohort) study: This is basically the prevalence surveys to be conducted with the selected cohort of children 6 months to 15 years – at baseline and before each of the subsequent MTTT rounds. b). The Survey involves using structured questionnaire to interview caretakers of children under five to solicit their views on the implementation process perceived benefits and challenges etc.** Though the target group is children from 6 months to 15 years of age, all parasitised adults will be cleared of the parasite during the interventions as well to reduce the parasite reservoirs. **Prevalence of malaria**

**trends in cohort group over the study period will reveal the effect of MTTT scale-up on the children 6month to 15 years.** Between interventions, the teams will conduct homes-based management of malaria for all febrile cases confirmed to be positive for malaria parasites. The challenges faced by the implementation team will be documented at every stage and discussed with all the stakeholders at every stage of the implementation.

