### **Timely treatment of suspected febrile malaria case in the community**

In order to render operational the home-based management component of the project, two volunteers will be selected from each community and trained on home-based management of malaria and be provided with the protocol, RDTs and ACTs. **The interventions will be carried out quarterly (see the timetable).** Between one MTTT intervention and the next trained community members will provide prompt home-based treatment for children and adults reporting signs and symptoms of malaria and confirmed to be carrying the parasite using RDTs. This will be done using national malaria management protocol. There will be monthly visits by the research team to supervise the community volunteers involved in home-based

management to ensure that the protocol is being respected as well as replenish their stocks. There is a need to visit the health facilities that service the community to enable tracking and linking of medical records with study participants (a master student is required for this component). The investigators hypothesize that a reduction in parasite load in the community will consequently lead to a reduction in the number of hospital malaria related consultations and admissions paving the way for pre-elimination. This will be realised by comparing baseline hospital malaria admission data to evaluation data. **MTTT has already been adopted by the NMCP as one of the control and elimination activities and the investigators are anticipating its being scaled-up in the country, and therefore documenting its implementation challenges will inform the decision in the future.**

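### The main objective, effect statement and cost comparison credit MTTT alone, but all seven communities also receive home-based testing and treatment, so the trial can describe only a before-after change under the two together

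*Protocol*

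**What the plan says.** Three places in the Protocol attach the result to MTTT alone.

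- Main objective: to "explore the impact of scaling up mass testing, treatment and tracking on malaria prevalence among children under fifteen years of age".
- Study Design: the prevalence trend in the cohort "will reveal the effect of MTTT scale-up on the children 6month to 15 years".
- Data Management and Analysis: the cost-benefit comparison sets past programme spending against spending if MTTT is implemented.

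Other places name a package. The hypothesis in the Rationale is what follows if the investigators "carry out MTTT in combination with home-based" management over two years, and the Project Summary says the same. Specific objective 1 pairs MTTT with home-based treatment for parasitaemia and hospital use. Expected outcome 1 repeats the pairing, for hospital admissions only.

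The second component reaches every community. Study Design: "Between interventions, the teams will conduct homes-based management of malaria for all febrile cases confirmed to be positive for malaria parasites". The section on timely treatment of febrile cases: "two volunteers will be selected from each community and trained on home-based management of malaria", and "trained community members will provide prompt home-based treatment for children and adults reporting signs and symptoms of malaria". The budget explanation for home-based management gives its purpose as clearing residual and missed parasitaemia between surveys.

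The precedent is also described in two ways. The Project Summary and Rationale present a fall from 25% to 1% as a result of MTTT in children. The Introduction says the study behind it "demonstrated that associating IPTc with home based management of malaria by community workers could clear more than 90% of the parasite pool" in the community.

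**The concern.** Home-based care acts on the endpoint the cohort measures. It treats RDT-positive children as well as adults, and the prevalence definition counts RDT-confirmed clinical malaria along with asymptomatic parasitaemia. Cohort surveys are taken at baseline and before each later round, so every survey after the first follows both a round and an interval of home-based care.

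If the main objective is reported as written, a change seen under two components will be credited to one. If the cost comparison is read literally, the cost of rounds alone could be set against benefits seen under rounds plus volunteers.

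**Working it through.** **1. Can the two components be separated?** Study participants gives MTTT to the whole population of the seven communities. The section on timely treatment places two volunteers in each of the same seven. Data Management and Analysis compares baseline with evaluation, and no control community is described.

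Take 7 communities × 6 surveys = 42 community-surveys, with an intercept, an MTTT indicator and a home-based indicator. The first survey, before any round, gives the row (1, 0, 0). Every later survey gives (1, 1, 1). The matrix has rank 2 for 3 parameters, and the two indicators correlate at 1.0. Only the sum of the two effects enters the data. Home-based care strictly follows the first round, but this does not help, because the first survey is free of both components and all later ones carry both.

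**2. Is the sum itself a causal effect?** Not from this comparison. At least four other influences are mixed in.

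- Season: the Work Plan puts the first survey in April to July 2017, across the May to June rains given under Study Area, and the sixth in November 2018 to February 2019, outside both rainy seasons.
- Ageing: one cohort is followed for about two years, and the Introduction says parasitaemia falls as children pass age five.
- Nets: Sample size mentions a 2016 head count made for a mass net distribution. The date of the distribution is not given, so its overlap with the study is unknown.
- Secular change.

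**3. How large is the second component, by the protocol's own forecast?** The budget totals reproduce:

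- Rounds: 2,250 + 1,575 + 675 + 450 + 900 = 5,850 courses.
- Home-based: 7 communities × 5 cases × 24 months = 840 courses.
- Home-based share: 840 / (5,850 + 840) = 840 / 6,690 = 12.6%.

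Home-based care gives 7 × 5 = 35 courses a month. The protocol describes rounds both as quarterly and as every four months, so one interval holds 35 × 3 = 105 or 35 × 4 = 140 courses. Setting one interval beside one round:

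| Courses in the round | Share with 105 home courses | Share with 140 home courses |
|---|---|---|
| 2,250 (first) | 105/2,355 = 4.5% | 140/2,390 = 5.9% |
| 1,575 (second) | 105/1,680 = 6.2% | 140/1,715 = 8.2% |
| 675 (third) | 105/780 = 13.5% | 140/815 = 17.2% |
| 450 (fourth to sixth) | 105/555 = 18.9% | 140/590 = 23.7% |

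The budget text also gives prevalences of 50, 35, 25, 15, 10 and 10%, which do not all match the counts it uses. Applied to 4,500 people they give 2,250 + 1,575 + 1,125 + 675 + 450 + 450 = 6,525 round courses. The overall share becomes 840 / (6,525 + 840) = 840 / 7,365 = 11.4%, and the 450-case rounds begin at the fifth. The conclusion is the same.

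**4. Home-based cost already budgeted.**

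- RDTs: 1,680 × $0.63 = $1,058.40.
- Treatment: 840 × $1 = $840.
- Volunteer allowances: 14 × $25.15 × 6 = $2,112.60.
- Total: $4,011.00.

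**The case against.** The strongest reply is that the package is already the stated hypothesis and specific objective 1. The Study Design sentence that credits MTTT is followed directly by one describing home-based management, so MTTT in the main objective may be shorthand. Specific objective 5 costs the intervention without excluding anything, and the home-based items are in the budget. Much of this stands: the repair is an alignment of wording, and no sample size or design feature changes. It does not remove the point, because the main objective and the effect sentence are what a report will be written against, and they name the component that the data cannot isolate.

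Four stronger readings are tempting and are not supported.

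- A reader might infer that the trial at least identifies the effect of the package. It does not, for the reasons in step 2.
- A reader might infer that the protocol offers an MTTT effect size as the basis for national scale-up. The section on timely treatment says the national programme has already adopted MTTT, and ties future decisions to documented implementation challenges. Nothing there proposes rounds without volunteers.
- A reader might take 19% to 24% as the part of the effect due to home-based care. It is a forecast of courses at all ages, for the 450-case rounds only.
- A reader might infer that the 25% to 1% result serves as a planning benchmark. It enters no calculation: the sample size uses 50% prevalence and the treatment forecast runs from 50% to 10%.

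**Conclusion.** The point holds as an inconsistency about which intervention is evaluated, with a consequence for what may be concluded. Because both components run in all seven communities after the first survey, an MTTT-only statement on prevalence or cost would be unsound at any sample size. What the trial can report is the change from baseline observed under MTTT rounds plus home-based management, without attributing that change causally to the package.

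The second component is not negligible: 12.6% of forecast courses overall, rising from about 4.5–5.9% at the first round to 19–24% at the 450-case rounds. These figures rest on the protocol's budget assumptions of five home-treated cases per community per month and its stated case counts. They say nothing about each component's share of any fall in prevalence, which cannot be identified here. The description of the precedent in the Project Summary and Rationale is an editorial error.

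**What to change.** 1. In Main objective, Study Design and Data Management and Analysis, name the evaluated intervention as *MTTT rounds plus home-based management between rounds*, in line with the hypothesis and specific objective 1.
2. State that conclusions are limited to the before-after change observed under that package.
3. In the cost comparison, include the home-based RDTs, treatment courses and volunteer allowances (about $4,011 on the budget's figures).
4. In the Project Summary and Rationale, describe the 25% to 1% result as IPTc plus home-based management, as the Introduction does.
5. Optionally, report treatment courses by route (round or home-based) for each interval between surveys. This would be descriptive only.

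Items 1 to 4 are wording changes and the use of costs already itemised. Item 5 may need a simple log, because the protocol does not describe a record of home treatments. The downside is a narrower claim than the effect of MTTT.
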